7.6.1 Adverse Events

An AE, for the purposes of this protocol, is the appearance of (or worsening of any pre-existing) undesirable sign(s), symptom(s), or medical condition(s) occurring after signing the informed consent, even if the event is not considered to be related to the study drug (study drug refers to the drug under evaluation [RAD001], and study treatment also refers to RAD001).

Adverse events will be assessed according to the CTCAE, version 3.0. If CTCAE grading does not exist for a particular AE, the severity of mild, moderate, severe, and life-threatening, or grades 1 to 4, will be used. The CTCAE grade 5 (death) will not be used in this study; rather, this information will be collected on the End of Treatment or Survival Information CRF page. All AEs will be coded by System Organ Class (SOC) and preferred term using the Medical Dictionary for Regulatory Activities (MedDRA), latest version.

Adverse event monitoring should be continued for at least 4 weeks following the last dose of study treatment. Adverse events (but not SAEs) occurring before starting study treatment, but after signing the informed consent form, are recorded on the Medical History/Current Medical Conditions CRF pages. Abnormal laboratory values or test results constitute an AE only if they induce clinical signs or symptoms, are considered clinically significant, or require therapy (e.g., any hematological abnormality that requires transfusion or cytokine treatment); and should be recorded on the Adverse Events CRF page under the signs, symptoms, or diagnosis associated with them. In addition, isolated abnormal laboratory values that are considered clinically significant (e.g., cause study discontinuation or constitutes in and of itself a SAE) should be recorded on the Adverse Events CRF page. Serious AEs occurring after signing the Informed Consent are recorded on the Adverse Event CRF page.

The occurrence of AEs should be sought by non-directive questioning of the patient at each visit during the study. Adverse events may also be detected when they are volunteered by the patient during or between visits or through physical examination, laboratory test, or other assessments.

As far as possible, each AE should be evaluated to determine:

1. The severity grade (CTCAE grades 1 to 4);
2. Its relationship to study drug (suspected/not suspected);
3. Its duration (start and end dates or if continuing at final exam);

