4. Action taken (no action taken; study drug dosage adjusted/temporarily interrupted; study drug permanently discontinued due to this AE; concomitant medication taken; non-drug therapy given; hospitalization/prolonged hospitalization);
5. Whether it is serious, where a SAE is defined as one which:
 - Is fatal or life-threatening;
 - Results in persistent or significant disability/incapacity;
 - Constitutes a congenital anomaly/birth defect;
 - Requires inpatient hospitalization or prolongation of existing hospitalization, unless hospitalization is for:
 - a) Routine treatment or monitoring of the studied indication, not associated with any deterioration in condition (specify what this includes);
 - b) Elective or pre-planned treatment for a pre-existing condition that is unrelated to the indication under study and has not worsened since signing the informed consent;

- c) Treatment on an emergency outpatient basis for an event not fulfilling any of the definitions of a SAE given above and not resulting in hospital admission;
 - d) Social reasons and respite care in the absence of any deterioration in the patient's general condition.
- Is medically significant, i.e., defined as an event that jeopardizes the patient or may require medical or surgical intervention to prevent one of the outcomes listed above.

Unlike routine safety assessments, SAEs are monitored continuously and have special reporting requirements; see [Section 8.1](#).

All AEs should be treated appropriately. Such treatment may include changes in the study drug treatment, including possible interruption or discontinuation, starting or stopping concomitant treatments, changes in the frequency or nature of assessments, hospitalization, or any other medically required intervention. Once an AE is detected, it should be followed until its resolution, an assessment should be made of any changes in its severity at each visit (or more frequently, if necessary), its suspected relationship to the study drug, any of the interventions required to treat it, and its outcome.

Information about common side effects already known about the study drug can be found in the IB or will be communicated between IB updates in the form of Investigator Notifications. This information will be included in the patient informed consent and should be discussed with the patient during the study as needed.

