8.1 Adverse Events

All AEs will be coded using the Medical Dictionary for Regulatory Activities (MedDRA®) Version 12.1 to provide the system organ class (SOC) and preferred term for each AE.

An adverse event will be defined as treatment emergent if it begins on or after the first day of dosing with study medication and no later than 30 days after the last dose of study medication. It is expected that adverse event monitoring will continue for at least 4 weeks after the last dose of study medication but new events occurring after the end of the treatment period will not be recorded on the CRF (unless they are serious or lead to death).

Since adverse events occurring prior to start of study or between signing informed consent and start of study medication should be considered as medical history, it is anticipated that all adverse events will be treatment emergent adverse events. However, in the event of any non-treatment emergent adverse events occurring, these will be indicated on the adverse event listings. Non-treatment emergent adverse events are defined as events that begin prior to the first day of dosing. If these events are Serious Adverse Events (SAEs) then they will also be summarized.

The number of patients experiencing each of the following will be summarized:

- At least one treatment emergent adverse event (TEAE)
- At least one SAE
- At least one SAE with a suspected relationship to study medication
- At least one adverse TEAE event leading to death
- At least one TEAE leading to modification of study medication
- At least one TEAE leading to permanent discontinuation of study medication
- At least one severe TEAE
- At least one TEAE with a suspected relationship to study medication

Serious adverse events will be indicated on the CRF, as will adverse events leading to modification or permanent discontinuation of study medication. The addition of non-drug therapy will not be classed as a modification of study medication.

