Adverse events resulting in death are not indicated on the CRF so will be defined as adverse events experienced by a patient who died, with a severity of life-threatening and an end date either missing or equal to the patient's date of death. If a patient has more than one adverse event identified as leading to death then a review by the Novartis medical contact should be performed to determine if each event led to death or whether one supersedes the other (e.g. underlying life threatening condition but patient actually died in an unrelated fatal accident).

All treatment emergent adverse events will be summarized by SOC and preferred term. If a patient experiences multiple events within a SOC the patient will only be counted once within that SOC. If a

patient experiences multiple preferred terms with in a SOC the patient will be counted for each preferred term but only once for each unique preferred term. Deaths reportable as SAEs and non-fatal SAEs will each be summarized by SOC and preferred term and also listed.

Deaths as reported on the Survival Information and Study Evaluation Completion CRF will be listed.

The handling of missing or partial start and end dates of adverse events, and missing assessments of severity and relationship is covered in Section 7.2.2.

All adverse events captured on the CRF will be listed, regardless of severity, relationship or treatment emergence.

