Preferred Term 3	xx (xx.x%)
ATC Class 2	xx (xx.x%)
Preferred Term 4	xx (xx.x%)
Preferred Term 5	xx (xx.x%)

Patients receiving more than one medication/therapy within an ATC Class or within an ATC Class and preferred term are only counted once.
Percentages are based on the number of patients in the Safety population.
Source: Listing 16.4-1.1

Table 14.5-1.1 (page 1 of 1)
Summary of Adverse Events
Population Safety

Events	Total N = xxxx n (%)
At least one treatment emergent adverse event	xx (xx.x%)
At least one serious adverse event	xx (xx.x%)
At least one adverse event leading to death	xx (xx.x%)
At least one adverse event leading to discontinuation of study medication	xx (xx.x%)
At least one adverse event leading to modification of study medication	xx (xx.x%)
At least one severe adverse event	xx (xx.x%)
At least one adverse event with suspected relationship to study medication	xx (xx.x%)

Percentages are based on the number of patients in safety population.
Source: Listings 16.5-1.1

Table 14.5-2.1 (page 1 of n)
Treatment Emergent Adverse Events by System Organ Class and Preferred Term
Population Safety

System Organ Class Preferred Term	Total N = xxxx n (%)
All treatment emergent adverse events	xx (xx.x%)
SOC 1	xx (xx.x%)
Preferred Term 1	xx (xx.x%)
Preferred Term 2	xx (xx.x%)
Preferred Term 3	xx (xx.x%)
SOC 2	xx (xx.x%)
Preferred Term 4	xx (xx.x%)
Preferred Term 5	xx (xx.x%)
Etc.	

Patients are counted once within each System Organ Class and Preferred Term or once within each System Organ Class for the summary row.
Percentages are based on the number of patients in safety population.
The table is sorted by system organ class then preferred term within system organ class alphabetically.
Source: Listing 16.5-1.1

Programming Note: Use same template for the following tables (but with different source listings).
- Table 14.5-2.2 Deaths Reportable as Serious Adverse Events by System Organ Class and Preferred Term
- Table 14.5-2.3 Serious Adverse Events by System Organ Class and Preferred Term

Table 14.6-1.1 (page 1 of 1)
 Summary of Survival and End of Study Status
 Population ITT

		Total N = xxxx n (%)
Alive at end of study	Overall	xx (xx.x%)
	With recurrence	xx (xx.x%)
	Without recurrence	xx (xx.x%)
Died	Overall	xx (xx.x%)
	Due to study indication	xx (xx.x%)
	Due to other reason	xx (xx.x%)
Died due to study indication	Already experienced recurrence	xx (xx.x%)
	No recurrence	xx (xx.x%)
Died due to other reason	Already experienced recurrence	xx (xx.x%)

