Programming note: Data ordered by country (alphabetically) then centre/patient identifier then by medications/therapies in order of start date (oldest first). Where unit or frequency have been recorded as "other" and then specified, it is only necessary to show the text in the specification (rather than Other: xxxxx). For route it appears from the CRF design that there is no further specification if "Other" is recorded so in this case the listing should just present "Other".

Listing 16.4-2.1 (page 1 of n)
Antineoplastic Therapy Since Discontinuation of Study Drug
All Treated Patients

Country/ Centre/ Patient	Regimen Number	Therapy Type	Medication/ Non-Drug Therapy	Start Date/ Day	Stop Date/ Day
XXXXXXXXXX/ XXXX-XXXX	1	Chemotherapy	XXXXXXXXXX	ddmmmyyyy/ xx	Ongoing
XXXXXXXXXX/ XXXX-XXXX	1	Immunotherapy	XXXXXXXXXX	ddmmmyyyy/ xx	ddmmmyyyy/ xx
XXXXXXXXXX/ XXXX-XXXX	1	Other: XXXXXXXXXX	XXXXXXXXXX	ddmmmyyyy/ xx	ddmmmyyyy/ xx

Day is calculated relative to the day of first dose of study medication.

Programming note: Data ordered by country (alphabetically) then centre/patient identifier. Therapy should be ordered by Regimen Number.

Listing 16.5-1.1 (page 1 of n)
 All Adverse Events
 All Treated Patients

Country/ Centre/ Patient	System Organ Class/ Preferred Term/ Verbatim	Serious Adverse Event	Grade	Relationship Suspected? / Action Taken	Resulted in Death?	Start Date/ Day	End Date/ Day	Treatment Emergent Event
XXXXXXXXXX/ XXXX-XXXX	XXXXXXXXXX/ XXXXXXXXXXXXXXXXXX/ XXXXXXXXXX	Yes	4	No/ No Action Taken	No	ddmmmyyyy/ xx	ddmmmyyyy/ xx	No
	XXXXXXXXXX/ XXXXXXXXXXXXXXXXXX/ XXXXXXXXXXXXXXXXXX	No	2	No/ Conmed Given	No	ddmmmyyyy/ xx	ddmmmyyyy/ xx	Yes
	XXXXXXXXXX/ XXXXXXXXXXXXXXXXXX/ XXXXXXXXXXXXXXXXXX	No	1	Yes/ Temporarily stopped study drug	No	ddmmmyyyy/ xx	ddmmmyyyy/ xx	Yes
	XXXXXXXXXX/ XXXXXXXXXXXXXXXXXX/ XXXXXXXXXXXXXXXXXX	No	1	No/ No action taken	No	ddmmmyyyy/ xx	Ongoing	Yes
XXXXXXXXXX/ XXXX-XXXX	XXXXXXXXXX/ XXXXXXXXXXXXXXXXXX/ XXXXXX	No	2	No/ Permanently stopped study drug	Yes	ddmmmyyyy/ xx	ddmmmyyyy/ xx	No

Day is calculated relative to the day of first dose of study medication.
 Adverse events are flagged as resulting in death if the patient dies and the AE end date is the day of death or is missing.

Programming note: Data ordered by country (alphabetically) then centre/patient identifier then by adverse event in order of start date (oldestfirst).

The following listings will follow this format:
 Listing 16.5-2.1 Deaths Reportable as SAEs - All Patients

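### SAP 8.1 and the Listing 16.5-1.1 footnote define an adverse event leading to death differently, and a single flagged event is counted as fatal without review

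*SAP*

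**What the plan says.** SAP 8.1 explains that the CRF carries no indicator for an adverse event (AE) that resulted in death, so one is derived. The derivation has three conditions: the patient died, the event was recorded "with a severity of life-threatening and an end date either missing or equal to the" patient's date of death. Protocol 7.6.1 gives the reason severity stops at life-threatening: "The CTCAE grade 5 (death) will not be used in this study".

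The footnote to Listing 16.5-1.1 states another rule. Events are "flagged as resulting in death if the patient dies and the AE end date is the day of death or is missing". It mentions no severity.

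Table 14.5-1.1 has the row "At least one adverse event leading to death" and the line "Source: Listings 16.5-1.1". The list of summaries in SAP 8.1 words the same row as "At least one adverse TEAE event leading to death", so the count is meant to be of treatment-emergent events.

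SAP 8.1 asks the sponsor's medical contact to review a patient only if more than one of that patient's events is flagged. It refers the reader to Section 7.2.2 for incomplete AE start and end dates. Section 7.2.2 is the RECIST section. Section 7.2.3 gives AE rules for missing severity and for start dates. It gives end-date rules for medications and for prior antineoplastic therapy, but none for AEs.

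**The concern.** With no CRF indicator and no grade 5, this derived flag is the only route the SAP sets out to the Table 14.5-1.1 count of patients with an AE leading to death. Two stated rules for one flag mean that the result depends on which text the programmer follows. A table built from the 8.1 rule may not match the listing it cites. A table built from the listing's flag would count events that 8.1 excludes.

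The review trigger is a separate weakness. The SAP's own example, a life-threatening condition in a patient who in fact died in an unrelated accident, shows that its authors know the flag can be wrong. The same error can occur with a single flagged event. Neither rule limits the time between the event and the death, so a grade 4 event left open on the CRF would be attributed as fatal to a patient who later died of progression. Describing the safety profile is a stated secondary objective, and readers look closely at deaths attributed to AEs.

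**Working it through.** **Inputs.** The 8.1 definition; the Listing 16.5-1.1 footnote; grades 1 to 4 (Protocol 7.6.1, where life-threatening is the highest category, taken here as grade 4); planned enrolment of 142 (SAP Section 3) and 110 (Protocol Section 4). The plan gives no figure of its own to reproduce.

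**Step 1: compare the rules for a patient who died.**

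| AE end date | SAP 8.1 flags | Footnote flags |
|---|---|---|
| Missing | grade 4 | grades 1–4 |
| Equal to death date | grade 4 | grades 1–4 |
| Complete and earlier | none | none |
| Partial | no explicit rule | no explicit rule |
| Ongoing | no explicit rule | no explicit rule |

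Four grades by five end-date states give 20 combinations. SAP 8.1 flags 1 × 2 = 2 of them and the footnote flags 4 × 2 = 8. The 8 − 2 = 6 on which they differ are grades 1 to 3 with an end date that is missing or equal to the death date. So the rules differ at 3 of the 4 grades whenever the end-date condition is met. A further 4 × 2 = 8 combinations have no explicit rule. These are counts of rule outcomes, not of patients.

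**Step 2: effect of one patient.** Assume that the Safety population equals planned enrolment. One patient moves the Table 14.5-1.1 row by 1/142 = 0.70 percentage points or 1/110 = 0.91 percentage points. The documents give no death rate for this trial and no rate of missing AE end dates, so the number of such patients cannot be derived.

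**Step 3: single flagged event.** Take a patient with one grade 4 AE, its end date never entered, who later dies of progression. All three 8.1 conditions are met. Only one event is flagged, so the review is not triggered, and the patient enters the count. Listing 16.6-1.4 shows a principal cause of death for each patient who died (study indication, or another cause in free text), but the derivation does not use it.

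**Step 4: partial end date (invented dates, for illustration).** Grade 4 AE, end date May 2011 with the day unknown, death on 14 May 2011.
- Treated as missing: flagged.
- Known part compared (May 2011 with May 2011): flagged.
- Imputed to the last day of the month, as Section 7.2.3 does for medications: 31 May is not 14 May, so not flagged.

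Three readings give two answers.

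**The case against.** The best defence is that 8.1 is the defining text and the footnote is shorthand that lost a condition. That may be how it arose, but the footnote is an instruction to programmers in the cited source, so it still needs correcting.

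Safeguards also surround these events. The SAE definition in Protocol 7.6.1 includes an event that "Is fatal or life-threatening", so a grade 4 event reported as SAP 8.1 describes should also have SAE reporting, causality assessment and follow-up. Site monitoring requires full verification of SAE documentation, and deaths are listed separately. This stands as mitigation, but none of it is linked to the flag. Table 14.5-2.2 (deaths reportable as SAEs) does not settle the count either, because the SAP does not say how its events are selected.

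The severity condition has its own cost: a fatal event recorded as grade 3 is never flagged and so never reviewed, whereas the footnote rule would catch it if the end date were missing or the death date. That is a fair argument for choosing deliberately. It is no argument for keeping two rules.

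Several stronger readings are tempting but not supported:
- **The mock row proves the wider rule is intended.** The listing's example row ("No/ Permanently stopped study drug") is grade 2, non-serious and not treatment emergent, yet marked as resulting in death. It holds placeholder values and shows at most that the shell follows the footnote.
- **Treatment emergence is part of the fatal-AE definition.** It is not among the three 8.1 conditions. It belongs to the summary row, and the listing has its own column for it.
- **Missing AE end dates have no rule at all.** A wholly missing end date is covered by both definitions. Ongoing is most naturally read as missing. Only explicit wording for ongoing and partial dates is lacking, which is a minor gap.

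**Conclusion.** The point holds in two parts. First, two stated definitions of an AE leading to death give different results for grade 1 to 3 events with a missing or death-date end date, and the table cites the listing that carries the wider one. Second, a single flagged event is counted as fatal with no specified check against the recorded cause of death. The AE end-date wording and the wrong cross-reference are a minor accompanying matter.

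The size is 0.70 to 0.91 percentage points per misclassified patient, on the Step 2 assumption about the Safety population. The total effect cannot be computed. A reader might infer that survival results or the death count are in doubt. They are not: PFS, OS and the listing of deaths from the survival CRF page do not use this flag, and the study tests no hypotheses. The correction should be made, but it concerns one descriptive safety count and its listing.

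**What to change.** 1. Use the three-condition 8.1 definition (death, life-threatening severity, end date missing or equal to the death date) for the flag and footnote of Listing 16.5-1.1, and bring the mock row into line.
2. Keep treatment emergence in its own listing column and apply it only when counting the Table 14.5-1.1 row, labelled as in the 8.1 list. Built into the flag, it would blank a fatal event that starts more than 30 days after the last dose, which 8.1 allows to be recorded.
3. Extend the existing review by the sponsor's medical contact to every patient with at least one flagged event, using the principal cause of death already recorded, and carry the reviewed result into both table and listing.
4. Correct the 8.1 cross-reference to Section 7.2.3. State there that an event ongoing at death counts as having a missing end date, and how a partial end date is compared with the death date.

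The cost is SAP wording, one footnote and mock row, and a short review of flagged deaths before database lock. No new data are needed. The review takes judgement, because a cause recorded as study indication or as free text will not always name an adverse event. It will not find fatal events graded below life-threatening; the SAP should state that limit.

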8.2 Cardiac assessments

Standard 12 lead ECG assessments will be performed at the investigator's discretion according to local practice, or if there are signs and symptoms of cardiotoxicity. These data will be listed.

8.3 Laboratory Tests

Each hematology, blood chemistry and serum lipid parameter will be summarized at the Baseline visit (Visit 1a), each cycle, the End of Treatment visit (last assessment up to and including 30 days after last dose date, including unscheduled assessments). The change from baseline will be presented at all post-baseline visits where this can be calculated.

Each coagulation parameter is collected at Screening Visit 1a and Day 1 of Cycle 2. These data will be listed.

Each urinalysis parameter will be collected at Screening Visit 1a and subsequently as clinically required. These data will be listed.

The hematology parameters collected are:

White blood cells (WBC), hemoglobin, hematocrit, platelets

Either: absolute neutrophils, absolute lymphocytes, absolute eosinophils, absolute basophils and absolute monocytes

Or: percentage neutrophils, percentage lymphocytes, percentage eosinophils, percentage basophils and percentage monocytes

The CRF allows for "other" differential counts to be recorded. These results will be listed only.

The blood chemistry parameters collected are:

Urea, blood urea nitrogen, creatinine, lactate dehydrogenase (LDH), total protein, fasting glucose, phosphorus, serum calcium, serum corrected calcium (calculated at baseline only), electrolytes (sodium, magnesium, chloride, and potassium), total bilirubin, gamma-glutamyl-transferase (GGT), albumin, alkaline phosphatase, alanine aminotransferase (ALT) (or SGPT), aspartate aminotransferase (AST) (or SGOT), uric acid

The serum lipid parameters collected are:

Total cholesterol, triglycerides, low-density lipoprotein (LDL), high-density lipoprotein (HDL)

The coagulation parameters collected are:

Prothrombin time (PT), International normalized ratio (INR)

All laboratory test results will be converted into Standard International (SI) Units by Data Management. Summary tables will present the results in SI Units.

The normal ranges for each parameter will also be included on the database so results can be calculated as being below, within or above the normal range.

Laboratory results will be graded using the Common Toxicity Criteria for Adverse Events (CTCAE) v3.0 document for each parameter where a CTC grade is defined. The parameters with grades defined are:

Hematology: WBC, hemoglobin, platelets and absolute neutrophils

Blood Chemistry: Creatinine, fasting glucose, sodium, magnesium, potassium, albumin, bilirubin, GGT, SGOT (AST), SGPT (ALT) and alkaline phosphatase

Serum Lipid Profile: total cholesterol, triglycerides

A shift table will be presented showing the change from screening to most extreme post-screening value (including the End of Treatment visit and any unscheduled assessments) in CTC grading.

In the event that an unscheduled laboratory test is performed the data from this test will be listed. Unscheduled visit results will only be summarized if the unscheduled visit supersedes the scheduled visit's results. I.e. if a scheduled visit is missed, or the laboratory sample is not taken, or there are no results from the laboratory sample, but there is an unscheduled visit occurring prior to the next scheduled visit then the results from the unscheduled visit should be used instead.

